4.1.2 SECONDARY ENDPOINTS

Secondary neurodevelopmental outcomes using age appropriate instruments will include the following:

- Visual spatial skill (VMI-6)
- Intelligence (WISC-V or WAIS-IV)
- Memory (WRAML-2 story memory subtest)
- Memory (WRAML-2 picture memory subtest)
- Executive function (D-KEFS verbal fluency, trail making subtext, and tower subtest)
- Language (WIAT-III oral language composite score) (listening comprehension and oral expression)
- Social cognition (Reading the mind in the eyes)

Secondary neurodevelopmental outcomes for probands assessed for autism include the following:

- ADOS-2

Brain structure/microstructure outcomes including but not limited to the following:

- Regional volumetric and cortical thickness measures
- Regional surface metrics
- Voxel-based DTI eigenvectors and apparent diffusion coefficient (ADC) values
- Resting state principal components

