5.3 STRATEGIES FOR RECRUITMENT AND RETENTION

Subjects will be recruited from among those in whom WES or WGS was performed in trios gathered by the PCGC Congenital Heart Disease Genetic Network Study (CHD GENES) or from subjects at Utah or UCSF/Gladstone with trios that have undergone WES or WGS during the PCGC grant period. The latter subjects may also be recruited to participate in CHD GENES during the consent process for this study. All cases (as defined in section 5.1) deemed eligible may be recruited. Controls (as defined in section 5.1) will be recruited and will be frequency matched to cases for CHD type, age category, and sex within each site to the greatest extent possible. The matching will include four CHD type categories (i.e. single ventricle with arch obstruction, single ventricle without arch obstruction, bi-ventricle with arch

obstruction, bi-ventricle without arch obstruction), two sex categories, and three age categories (8-12, 13-17, 18+). This results in 24 unique combinations of CHD type, sex, and age category within each of the sites. A list of cases and controls will be generated for each site. To the extent possible, study personnel at the site that will have direct contact with the subjects should remain blinded as to which subjects are cases and controls. The site lists will be presented such that the blind IDs are presented in random order of cases and controls. Sites should approach each of the subjects on their lists, and subjects/families can be approached in any order. The ACC will monitor the balance of cases and controls within each site and across all sites to determine if any modifications in recruitment are necessary due to severe imbalance; if so, the ACC will work with individual sites to restore balance. Of note, some sites may be recruiting controls to match cases at other sites. Because we are using a frequency matching process in this protocol, no specific control is matched to a specific case, but rather we aim to have approximately the same number of controls as cases within each of the 24 strata.

The medical record will be reviewed or the subject's cardiologist will be contacted before initiating contact with subjects or their parent/guardian to be sure that the subject is alive.

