The primary analysis for all endpoints (primary and secondary) will compare patients with and without known deleterious mutations and will include the matching factors of site, CHD type, sex, and age category using a generalized analysis of variance model. Because socioeconomic status (SES) has a proven effect on neurodevelopmental performance in virtually all published studies, we will also adjust for this variable in all models. An appropriate link and distribution function will be used depending on the distribution of the outcome variable (e.g. identity link and normal distribution for normal data, logit link and binomial distribution for dichotomous data). If assumptions of the model are violated, appropriate transformations will be performed (e.g. log, square root, rank) in order to satisfy the assumptions. Models supporting the primary analysis will include variables that may be associated with adverse neurodevelopment as covariates, (e.g., maternal education, history of prematurity or early term birth, number of open heart surgeries, number of cardiac catheterizations, number of serious adverse events, etc.). We will perform separate analyses for each potential covariate that include the variable, along with the matching factors and SES, and consider those variables associated with endpoint at a p -value <0.1 as covariates in stepwise generalized linear models. Collinearity will be assessed. The primary analyses and all secondary analyses will be conducted at the two-sided 5% level of significance. No multiple testing adjustments will be used for the secondary outcomes, although it is recognized that results of these tests should be interpreted with caution. Exploratory analyses of effect modification by neuro-resiliency polymorphisms may be performed by including interaction terms in the models.

MRI Outcomes:

MRI outcomes will include measures based on voxel-level analyses (e.g. grey matter volumes, regional cortical thickness, etc.) and outcomes that are summarized at the patient level (e.g. mean global FA). For unadjusted voxel-level analyses, two-sample t-tests (with appropriate transformations, if needed to satisfy the assumptions of the analyses) or Wilcoxon Ranks sum tests will be conducted to identify voxels that are significantly different between the two groups. P-value adjustments for multiple testing will be done to control the false discovery rate at 5% for voxel-level analyses for each MRI measure.

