Using clinical and demographic variables that are differentially distributed between the two groups (as identified by $p < 0.10$ in univariate analyses) as potential covariates, adjusted analysis at the voxel level will be conducted using stepwise generalized linear modeling with appropriate distribution and link functions.

Unadjusted comparisons of MRI outcomes measured at the patient level for the two groups will be made using the two-sample t-test or Wilcoxon Rank Sum test. Additional analyses for patient level MRI outcomes will include adjustment for matching factors (site, sex, CHD type and age category) and other demographic and clinical characteristics that are differentially distributed between groups (as identified by $p < 0.10$ in univariate analyses) using stepwise regression models. Collinearity will be assessed and transformations used, if required, to satisfy the assumptions of the analyses. All tests will be conducted at the two-sided, 5% level of significance and no adjustment will be made for multiple testing for the MRI outcomes measured at the patient level.

Alternative approaches for analyzing the MRI and genetic data to determine if there is a significant association between genetic variants and brain MRI endophenotype in patients with CHD will be based on the state of the art statistical approaches that are available when the data base for this protocol is closed. The statistical analysis of MRI and genetic data is a rapidly evolving field and it is expected that more sensitive statistical approaches will be developed during the course of this study.

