10.3 SAMPLE SIZE

Mean total composite achievement score will be compared for subjects with and without deleterious mutations using a two-sided, two-sample test conducted at the 0.05 level of significance. The standard deviation of achievement score is assumed to be 15 in each group. With 176 subjects with genetic mutations and 175 without mutations, we have 80% power to detect a difference in means of 4.5, or 0.3 standard deviations. If the true effect size is 0.5 standard deviations, samples of 64 subjects in each group would provide 80% power to detect a mean difference of 7.5.

Similarly, the following table provides the samples size required to attain 80% power to detect the specified effect size (i.e. standardized difference between means) between the two groups for any continuous neurodevelopmental or MRI patient level outcome at the two-sided 5% level of significance.

Effect Size	Sample Size for each group for 80% Power using Two-sample T-test
0.3	176
0.4	100
0.5	64

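### Patient-level MRI outcomes lead with an unadjusted test, although the protocol elsewhere makes the matching-factor and SES model primary for all primary and secondary endpoints

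*Protocol*

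**What the plan says.** Three parts of the Protocol bear on this.

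- **4.1.2 Secondary Endpoints** includes the imaging measures: "Brain structure/microstructure outcomes including but not limited to the following".
- **10.2.1, under Neurodevelopmental Outcomes**, states "The primary analysis for all endpoints (primary and secondary) will compare patients with and without known deleterious mutations". That analysis includes site, CHD type, sex and age category, and SES is to be adjusted for in every model.
- **10.2.1, under MRI Outcomes**, states "Unadjusted comparisons of MRI outcomes measured at the patient level for the two groups will be made using the two-sample t-test" or the Wilcoxon rank sum test. It continues: "Additional analyses for patient level MRI outcomes will include adjustment for matching factors (site, sex, CHD type and age category", together with characteristics that differ between groups at p < 0.10, by stepwise regression. SES is not named. On error control: "All tests will be conducted at the two-sided, 5% level of significance and no adjustment will be made for multiple testing" for these outcomes.

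10.3 sizes patient-level MRI outcomes with a two-sample t-test table: 176, 100 and 64 per group for 0.3, 0.4 and 0.5 SD.

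**The concern.** Taken literally, the neurodevelopmental text makes the adjusted model primary for MRI outcomes, because they are secondary endpoints. The MRI text puts the unadjusted test first and makes adjustment additional. Someone writing the analysis plan could cite either.

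The order matters because controls are frequency matched on CHD type, sex and age category within site. If matching holds, an unadjusted test leaves the variance of those factors in its error term and loses power. If it does not hold, differences between sites enter the group contrast. The Protocol gives reasons why the scanned subset may be less balanced than the whole cohort:

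- 5.3 notes "Of note, some sites may be recruiting controls to match cases at other sites".
- Only selected centers scan (7.1.1).
- Subjects with contraindications, or who decline or would need sedation, are not scanned (5.2, 7.1.1.2).
- Case or control status is finally settled at study end, after matching (10.2.1).

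Aim 2 is one of only two aims, so a borderline result could turn on which test is read.

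**Working it through.** **1. The Protocol's own figures.** Inputs from 10.3 are two-sided 5%, 80% power and the t-test. For the primary outcome, "The standard deviation of achievement score is assumed to be 15 in each group" and "we have 80% power to detect a difference in means of 4.5, or 0.3 standard deviations". With n = 2(1.96 + 0.8416)²/d², the normal approximation gives 175, 99 and 63 per group for d = 0.3, 0.4 and 0.5. The noncentral t gives 175.4, 99.1 and 63.8, which round up to 176, 100 and 64. Power with 176 and 175 at 0.3 SD is 80.0%. The table reproduces.

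**2. Assumed inputs.** The Protocol gives no MRI subset size, number of scanning sites or MRI variance components. Assumed here: n = 64 per group (the 0.5 SD row), four equal sites, site share s = 0.10 to 0.30 and age-category share a = 0.10 to 0.20 of a total variance of 1. Let R² = s + a, so R² runs from 0.20 to 0.50.

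**3. Matching holds.** The group difference then has variance 2(1 − R²)/n, but the unadjusted test estimates it as about 2/n.

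- Unadjusted size = 2Φ(−1.96/√(1 − R²)). R² = 0.20: 2Φ(−2.19) = 2.8%. R² = 0.50: 2Φ(−2.77) = 0.6%.
- With d√(n/2) = 0.5 × √32 = 2.83, unadjusted power = Φ((2.83 − 1.96)/√(1 − R²)). R² = 0.20: 83%. R² = 0.50: 89%.
- Adjusted power = Φ(2.83/√(1 − R²) − 1.96). R² = 0.20: 89%. R² = 0.50: 98%.

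Simulation agrees: unadjusted size about 0.5-2.6% and power 82-88%, against about 5% and 88-98% adjusted. The tests disagree on significance in about 5-11% of simulated trials at 0.5 SD.

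**4. Matching fails by site.** Let case shares alternate between sites at 0.5 + k and 0.5 − k. The fractions of cases and of controls at a given site then differ by k. With independent site effects of variance s, these add 4k²s to the variance of the difference. In units of 2/n that is V = 4k²s/(2/64). Size is about 2Φ(−1.96/√(V + 1 − R²)).

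- 60/40 (k = 0.1): s = 0.10, a = 0.10 gives V = 0.128 and size 4.2%. s = 0.30, a = 0.20 gives V = 0.384 and size 3.7%. Simulation: 3.6-4.8%.
- 70/30 (k = 0.2): s = 0.10, a = 0.10 gives V = 0.512 and size 8.7%. s = 0.30, a = 0.20 gives V = 1.536 and size 17%. Simulation: about 9-23%, depending on how the site effects are drawn.

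The adjusted model stays at about 4-5%. Simulated disagreement at 0.5 SD is about 10-18% at 60/40 and 19-34% at 70/30.

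**5. A second model.** With 24 strata explaining 10-50% of variance, at the Protocol's own sample and effect sizes, unadjusted size was 0.6-3.9% under exact matching. It was 6-27% when cases were tilted towards higher-scoring strata. Adjusted size was 4.3-5.7% throughout. No run gave two significant results of opposite sign.

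**The case against.** The best defence is that there is no contradiction. The all-endpoints sentence stands under Neurodevelopmental Outcomes, just after that part lists its own outcomes, and SES is justified by its effect on neurodevelopmental performance. MRI has its own heading and methods. That reading is fair, and it makes the conflict arguable. But it leaves the unadjusted test leading Aim 2's patient-level outcomes, which is the weaker order for this design. The t-test sizing in 10.3 does not settle intent, since the same section sizes the WRAT-4 score that way although its primary analysis is adjusted.

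Several stronger readings are tempting but not supported:

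- *Two rival deciding analyses.* The MRI text does give an order; it calls adjustment additional.
- *Opposite conclusions.* The disagreement is significant versus not significant. Under exact balance the two estimates coincide, and the stratum simulation showed no reversal.
- *An unadjusted test that produces false positives.* This needs marked imbalance. 5.3 matches within site as far as possible and has the coordinating center monitor and restore balance, and 7.1.1.2 harmonizes scanners. Nothing in the Protocol points to 70/30.
- *An underpowered MRI comparison.* When matching holds, unadjusted power of 82-88% still exceeds the planned 80%. The loss is relative to the adjusted model.

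It can also be said that ranking analyses of secondary outcomes belongs in the statistical analysis plan. That would answer silence. Here the Protocol states an order for MRI that sits badly with its own general statement.

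**Conclusion.** The point holds as a matter of consistency and efficiency. The Protocol's general statement, combined with 4.1.2, makes the adjusted model primary for MRI outcomes, while the MRI text leads with an unadjusted test. If the general statement is confined to neurodevelopment, the unadjusted test simply leads, and it should not.

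The firmer cost is the power forgone when matching works: 82-88% against 88-98% at 0.5 SD, with a true size of about 0.5-2.6% instead of 5%. Inflation to about 9-23% is conditional on a 70/30 split by site; at 60/40 size is roughly nominal. All of these rest on the assumed subset size, number of sites and variance shares.

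The importance is moderate, because MRI outcomes are secondary and the WRAT-4 primary analysis is clearly adjusted. A reader might also infer that choosing one model would give Aim 2 a single primary contrast. It would not: the list of MRI outcomes is open-ended and the patient-level tests carry no multiplicity adjustment.

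**What to change.** In the MRI part of 10.2.1, state that the primary analysis of each patient-level MRI outcome is the model already described for the other endpoints: group plus site, CHD type, sex, age category and SES, all forced in without selection. Label the unadjusted t-test or Wilcoxon result and the stepwise model as supportive.

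This is a wording change, best made before the final group classification is linked to outcomes. Site and the matching factors are already in the planned additional analysis, and SES adjustment is already planned for the study. The statistical cost is a few degrees of freedom. With 128 subjects, four sites and SES as one term (both assumed), the model has 1 + 1 + 3 + 3 + 1 + 2 + 1 = 12 parameters (intercept, group, site, CHD type, sex, age, SES), leaving 116 residual degrees of freedom against 126 for the t-test.

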10.3 SAMPLE SIZE

Mean total composite achievement score will be compared for subjects with and without deleterious mutations using a two-sided, two-sample test conducted at the 0.05 level of significance. The standard deviation of achievement score is assumed to be 15 in each group. With 176 subjects with genetic mutations and 175 without mutations, we have 80% power to detect a difference in means of 4.5, or 0.3 standard deviations. If the true effect size is 0.5 standard deviations, samples of 64 subjects in each group would provide 80% power to detect a mean difference of 7.5.

Similarly, the following table provides the samples size required to attain 80% power to detect the specified effect size (i.e. standardized difference between means) between the two groups for any continuous neurodevelopmental or MRI patient level outcome at the two-sided 5% level of significance.

Effect Size	Sample Size for each group for 80% Power using Two-sample T-test
0.3	176
0.4	100
0.5	64

10.4 MEASURES TO MINIMIZE BIAS

10.4.1 ENROLLMENT/ RANDOMIZATION/ MASKING PROCEDURES

The study does not involve randomization, blinding, or masking.

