5 STUDY ENROLLMENT AND WITHDRAWAL

5.1 SUBJECT INCLUSION CRITERIA

To be eligible for the study, subjects must meet all of the following criteria:

1. Subjects in whom WES or WGS has already been performed, either during the CHD GENES study or, for new centers (Utah or UCSF/Gladstone), after trios in existing biobanks undergo analysis by WES or WGS during the PCGC2 grant cycle

2. Presence of deleterious mutations (damaging de novo mutations or stringently defined deleterious missense mutations) identified on sequencing (Cases) OR absence of such known deleterious mutations (Controls)
3. Males or females, age ≥ 8 years
4. Diagnosis of CHD
5. Informed consent obtained

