7 STUDY PROCEDURES AND SCHEDULE

7.1 STUDY PROCEDURES/EVALUATIONS

7.1.1 STUDY SPECIFIC PROCEDURES

A subject will be considered enrolled following documentation of informed consent.

Following informed consent (as outlined in section 13.3) the following procedures will be performed as part of the study and should occur within 6 months of the first in-person evaluation:

- Demographic, medical history, concomitant medication and clinical characteristics data collection
- Neurocognitive and Behavioral Health Evaluation
- Brain MRI Imaging, in a subset of enrolled subjects

Data Collection

- Review of Inclusion/Exclusion criteria
- Medical history will be obtained by interview with the subject/parent/legal guardian as well as review of the medical chart. Medical history will include collection of WES or WGS results and other relevant data from the CHD GENES database, where available.
- Measurement of subject height and weight
- Concomitant Medication Review
- Collection of primary care physician name (if subject consents for results to be shared)

Brain MRI Imaging

- Brain MRI imaging will be performed in a subset of subjects, i.e., those enrolled at selected centers who have no contraindications to having brain MRI.
- Brain MRI imaging without contrast or sedation will be performed.
- Institutional policy for pregnancy testing prior to research MRI will be followed.
- Details of the brain MRI imaging parameters will be defined in the study specific Manual of Operations. The following MRI sequences will be performed:
 - Structural MRI
 - Diffusion Tensor MRI
 - Resting State Functional MRI
- Subjects unable or unwilling to have the brain MRI imaging may still be enrolled into the study to collect neurocognitive and behavioral health endpoints.

Neurocognitive and Behavioral Health Evaluation

- Neurodevelopmental assessment of the subject will be performed by a licensed psychologist or supervised psychometrician at each site according to Table 5 below. Multiple areas will be assessed including intellectual functioning, academic (reading and math) functioning, language, memory, attention/executive functioning, visual spatial, fine motor, social functioning, adaptive skills, emotional/behavioral functioning, and quality of life.

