7.3.3 SCHEDULE OF EVENTS TABLE

Procedures	Screening ^a	Study Procedures ^a
Informed Consent	X	
Review of Inclusion/Exclusion Criteria	X	
Measure subject height/weight		X
Review of Medical History		X
Collect Concomitant medications/medication history/prior WES results		X
Subject ND test battery ^b		X
Brain MRI ^c		X
Parent/Teacher ND test battery		X ^d
Yearly follow up phone call for up to 5 years (see section 13.4. m)		X

^aAll screening and study procedures *may* occur on the same day. However, if needed, the ND testing and MRI may be scheduled over 2 or more visits with a maximal interval between testing of 6 months.

^bIf ND testing and brain MRI are performed on the same day, ND testing should be completed prior to performing the Brain MRI.

^cIn females of childbearing age, pregnancy testing may be performed per institutional procedure before brain MRI. Participants positive for pregnancy will not undergo the brain MRI.

^d Parent/Teacher questionnaires may be mailed to the parent up to 3 months prior to the in-person ND testing, or may be done at the time of the ND testing.

If ND testing and/or brain MRI images are deemed incomplete, repeat testing may occur at the discretion of the PI, if feasible, and if the participant agrees to the repeat testing. If repeat testing occurs, a process note will be placed in the study subject binder documenting the discussion and the participant/parent/LAR agreement to repeat testing.

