Under the leadership of the PCGC's "Disclosure of Results" Committee, we will include an option in the CHD Brain and Genes consent form asking subjects and their families whether they would like us to inform them and/or their doctor about whether they/their children were found to carry CHD or neurodevelopment-related genetic variants considered to be pathogenic at the end of the study. We will state that to find out whether the research tests result might be relevant to them/their child's care, it must first be confirmed in a CLIA-approved laboratory using new blood or saliva samples. We will offer participants the ability to consult with a genetic counselor or geneticist before having the clinical test or after the results are known, and will help participants and their physicians in this process. For participants who elect to be informed of their genetic variants, the cost for obtaining a new sample for testing, the testing of the sample in the CLIA lab, and the genetic counseling will be paid for as part of the research study and will not be charged to the patient.

There are several reasons for disclosing results at the end of the study to those study participants who wish to be informed about pathogenic CHD or neurodevelopmental variants. The clinical importance of many of the variants is unknown; indeed, our study results will provide insights on the association of these mutations with adverse outcomes. In addition, the final "grouping" of subjects into mutation positive or negative groups could change over the course of the study in light of new knowledge, including results of whole genome sequencing. The ultimate classification of subjects into the two groups will not take place until the final year of the study. Although subjects with known pathogenic mutations in previously established CHD genes will have been excluded from this protocol at study onset, we expect that we will have discovered new pathogenic mutations by the end of the study period. A further advantage of disclosure of results at the end of the study is that knowledge of the presence of a mutation could influence the results of subjective tests, like quality of life measures, and even responses to questions about cognitive function and behavioral measures.

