14 DATA HANDLING AND RECORD KEEPING

14.1 DATA COLLECTION AND MANAGEMENT RESPONSIBILITIES

Data collection is the responsibility of the clinical trial staff at the site under the supervision of the site PI. The investigator is responsible for ensuring the accuracy, completeness, legibility, and timeliness of the data reported.

All source documents should be completed in a neat, legible manner to ensure accurate interpretation of data. Black ink is required to ensure clarity of reproduced copies. When making changes or corrections, cross out the original entry with a single line, and initial and date the change. **DO NOT ERASE, OVERWRITE, OR USE CORRECTION FLUID OR TAPE ON THE ORIGINAL.**

The ACC will be responsible for the creation, distribution and training materials related to all CRFs that are not the standardized instruments listed in 7.1.1. The ACC will provide the sites with CRF Completion Guidelines and Data Entry Guidelines specific to each CRF to ensure consistent and accurate collection and entry of data.

All data collected at the site (including AEs, concomitant medications, and expected adverse reactions data) will be entered by trained trial site staff into the Medidata Rave CDMS, a 21 CFR Part 11-compliant data capture system provided and managed by the ACC. The CDMS includes password protection and internal quality checks, such as automatic range checks, to identify data that appear inconsistent, incomplete, or inaccurate. Integrated into the data entry system are real time validations, including both inter- and intra-instrument data checks. Inconsistent or questionable values are flagged during entry, and a query is automatically generated to the data entry client. These queries provide the information necessary to investigate any data entry errors or resolved questions regarding out-of-range or questionable values. Second-level query tracking allows monitors and data managers real time access to unresolved queries as well as the date and time of query generation and resolution. In some instances, with prior approval from the study Steering Committee, some data to be used for additional sub-analyses may be entered and stored in a study specific REDCap or other appropriate database. ACC staff are responsible for the tracking of data entry at each site to ensure timely submissions and query resolution so data are available as close to real-time as possible for all reporting and analysis done during the execution of the protocol.

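### Section 10.4.1 denies any masking although Section 5.3 asks site staff to stay blinded, and nothing in the visit procedures keeps sequencing results from those who test and score

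*Protocol*

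**What the plan says.** Section 10.4.1 is the only text under the protocol's heading on minimizing bias. Its single sentence is "The study does not involve randomization, blinding, or masking".

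Section 5.3 describes masking at the sites. It says that "study personnel at the site that will have direct contact with the subjects should remain blinded as to which subjects are cases and controls", and opens that sentence with a best-effort qualifier. It also gives a mechanism: "The site lists will be presented such that the blind IDs are presented in random order of cases and controls".

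The visit procedures bring genetic information to the site:

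- Section 7.1.1, data collection: "Medical history will include collection of WES or WGS results and other relevant data from the CHD GENES database, where available".
- Section 7.3.3, marked in the study-procedures column: "Collect Concomitant medications/medication history/prior WES results".
- Section 5.1, inclusion criterion 2, turns on mutation status: "Presence of deleterious mutations (damaging de novo mutations or stringently defined deleterious missense mutations) identified on sequencing (Cases) OR absence of such known deleterious mutations". The second branch defines the control group. Sections 7.1.1 and 7.3.3 both list the eligibility review.
- Section 14.1: data collected at the site "will be entered by trained trial site staff into the Medidata Rave CDMS", and each site has full access to its own data.

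The outcomes are produced at the same sites. A site psychologist or supervised psychometrician gives the battery (Section 7.1.1) and site staff score it (Section 7.1.2). The footnote to Table 5 lets the coordinator, after consulting the site psychologist and with confirmation by the site's principal investigator, call for the ADOS-2 when the SRS-2 total is below 60.

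**The concern.** Exposure here is genotype and cannot be randomized. Keeping examiners and scorers unaware of it is one of the few design protections against expectation bias, and Section 10.1 states a directional hypothesis: more abnormality in mutation carriers. The protocol both asks for this protection and says that it does not exist.

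There are two practical consequences. First, Section 14.3 defines a deviation as noncompliance with the protocol, good clinical practice or the manual. A site relying on Section 10.4.1 could regard disclosure of case status to an examiner as compliant and never log it. Second, even a site that follows Section 5.3 gets no instruction on how to collect sequencing results without undoing the blind list. Any tilt that enters at testing or scoring is part of the recorded score, and the analysis cannot remove it.

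**Working it through.** **1. Do the two statements conflict?** Section 5.3 sets a best-effort aim for staff with direct subject contact and supplies a tool for it. Section 10.4.1 denies blinding and masking without exception. The qualifier in Section 5.3 softens the aim but does not reconcile the two, because a best-effort blind is still a blind.

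**2. Is there a route to unmasking?**

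| Step | Who, according to the protocol | Section |
|---|---|---|
| Collect sequencing results | not stated; listed as a study procedure | 7.1.1, 7.3.3 |
| Check mutation-status criterion | not stated; part of eligibility review | 5.1, 7.1.1, 7.3.3 |
| Enter site data; view own-site data | site staff; site | 14.1 |
| Administer tests | site psychologist or psychometrician | 7.1.1 |
| Score tests | site staff | 7.1.2 |
| Trigger ADOS-2 below the SRS-2 cutoff | coordinator, psychologist, site investigator | 7.1.1.1 |

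No section says that the first two rows must be done by people other than those in the last three. Nor is result collection placed after testing: a footnote in Section 7.3.3 allows all screening and study procedures on one day. The route is open, but no section says that it is used.

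**3. The plan's own sample-size figure.** Inputs from Section 10.3: SD 15, 176 and 175 subjects, difference 4.5, two-sided 0.05.

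- Standard error = 15 × √(1/176 + 1/175) = 1.601.
- Noncentrality = 4.5 / 1.601 = 2.81. The two-sample t-test power is 80.0%, as stated.
- Exact t-test sizes for effects 0.3, 0.4 and 0.5 are 175.4, 99.1 and 63.8 per group, which round up to the tabled 176, 100 and 64.

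**4. Illustration of size.** The documents give no bias figure, so the tilt *b* (average difference between groups created by administration or scoring) is an assumption. With no true difference, the chance of a significant result is P(|T| > t₀.₉₇₅), where T is noncentral t with 349 degrees of freedom and noncentrality b / 1.601.

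| b (points) | in SD | share of 4.5 | chance of a significant result |
|---|---|---|---|
| 0 | 0 | 0% | 5.0% |
| 0.75 | 0.05 | 17% | 7.5% |
| 1.5 | 0.10 | 33% | 15.4% |
| 2.25 | 0.15 | 50% | 28.9% |
| 3 | 0.20 | 67% | 46.4% |

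Here *b* is an average over all 351 subjects. If examiners knew the status of only half of them, an average of 1.5 points would need 1.5 / 0.5 = 3 points among those subjects. The table uses the WRAT-4 because the protocol gives its SD and target difference, not because it is the outcome most at risk.

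**The case against.** The strongest reply is that no unmasking has been shown. Section 7.1.1 says the results come from the CHD GENES database where available, and Section 13.4.1 foresees linking the neurodevelopmental and MRI data to CHD GENES genetic data, which could be done centrally. Inclusion criterion 2 accepts either presence or absence of a mutation, so a site might tick it from the list alone. Final grouping is left to the genetic team at study end (Sections 8.7 and 10.2.1). All this stands, and it limits the point to an exposure that is not prevented. It does not close the route, since initial case status and sequencing results exist from enrollment.

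The primary outcome is also fairly robust: a norm-referenced achievement test (Appendix A), given by evaluators certified by video review (Section 7.1.1). That stands too.

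Several stronger readings are tempting but unsupported:

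- *The visit procedures reveal case status to examiners.* No section says that the person who collects the results tests or scores.
- *The protocol admits examiner bias.* Section 8.7 does say that "knowledge of the presence of a mutation could influence the results of subjective tests", but as a reason to delay disclosure to participants. It concerns respondents, and the protocol acts on it. The same logic may extend to examiners, but that is the reader's inference.
- *Exclusions 3 and 5 disclose the group.* Exclusion 3 applies to cases and controls alike, and exclusion 5 can be judged from the brain injury without the genotype.
- *All behavioral outcomes are exposed to site scoring judgment.* The Vineland-3, for example, is completed by the caregiver (Section 7.1.1.1).
- *MRI outcomes are equally exposed.* Those images go to the MRI Core for processing (Section 14.1), and no masking fault is shown there.

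**Conclusion.** The contradiction between Sections 10.4.1 and 5.3 is real and needs correcting. The gap in the visit procedures is also real: nothing keeps sequencing results from those who test, score or decide on the ADOS-2. Whether they would see those results cannot be settled from the protocol.

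The exposure matters most for ADOS-2 referral and scoring and for oral expression, and less for the WRAT-4. The error rates of 7.5% at 0.75 points and 15.4% at 1.5 points rest on an assumed tilt, no true difference, and the Section 10.3 design figures. They show that a tilt well below the 4.5-point target would matter; they do not estimate what will happen. A reader might infer that the primary result is compromised, and the documents do not support that. The change is still best made before testing, because masking cannot be restored once a score is recorded.

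**What to change.** 1. Replace the sentence in Section 10.4.1 with text that agrees with Section 5.3: the study is not randomized; examiners, scorers and site staff with direct subject contact are, to the extent possible, masked to case or control status until the neurodevelopmental data are locked. Final classification by the genetic team before database lock is compatible with this.
2. Amend Sections 7.1.1 and 7.3.3 so that sequencing results and the mutation-status criterion are handled centrally, through the linkage that Section 13.4.1 already foresees, or by named site staff who neither test nor score. Restrict access to those fields in the site's data view accordingly.
3. Record known unmasking of an examiner, scorer or ADOS-2 decision-maker, so that its extent can be reported.

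The cost is protocol wording and some separation of roles at the sites, which may be awkward where the team is small. A few subjects whose clinical chart reveals the genotype will remain unmasked and should be recorded as such. The sample size and the analysis model do not change.
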